6.2.2.2. Biologically Effective Dose

Pharmacokinetic (PK) and PD data will be used for estimating the biologically effective dose (BED). For the purpose of this study, the BED is defined as the lowest dose that achieves a minimum of 30 to 50% inhibition of CDK4/6 (measured by pRb and topoII α) in surrogate tissues (hair follicles or skin) at steady state. This level of CDK4/6 inhibition corresponds to that observed in mouse preclinical experiments at the lowest dose achieving tumor growth delay. Nonclinical PK/PD modeling predicts that a dose of 150-300 mg of LY2835219 administered every 24 hours will produce the minimum level of CDK4/6 inhibition that has been associated with tumor growth delay in preclinical efficacy studies.

6.2.3. Dose Confirmation Phase (Parts B, C, D, E, F, and G)

After the MTD has been identified in Part A, at least 15 and up to 45-60 patients will be enrolled in each of the 6 tumor-specific expansions: Part B (non-small cell lung cancer), Part C

(glioblastoma multiforme), Part D (breast cancer), Part E (melanoma), Part F (colorectal cancer), and Part G (HR+ breast cancer).

During the dose confirmation phase, patients may enroll concurrently and will be treated at a dose no greater than the MTD (200 mg every 12 hours). Patients enrolled under JPBA amendment (f) who are still receiving LY2835219 at a dose of 150 mg every 12 hours may, at the discretion of the investigator, be escalated to 200 mg every 12 hours. Patients enrolled under JPBA amendment (g) or subsequent amendment should initially receive LY2835219 at a dose of 200 mg every 12 hours. For all patients, dose adjustments are permitted as outlined in Section 6.2.4.1.

If DLT-equivalent toxicities occur in 33% or more of patients within a tumor-specific cohort expansion, then investigators and the Lilly CRP will assess the nature and severity of these toxicities. No additional patients will be accrued until this safety review is completed and a decision is made either to continue at the current dose or to deescalate the dose and define a new dose for the expansion phase. The safety review and decision will be documented in writing.

During the dose confirmation phase, paired tumor biopsies should be obtained, whenever clinically feasible, before (Day -14 to Day -4) and after (Day 8 to Day 22) administration of study drug in Cycle 1.

6.2.4. Dose Adjustments

6.2.4.1. Dose Adjustments

Table JPBA.6.2 is a guidance for management of treatment-emergent, related, and clinically significant toxicities of LY2835219.

Table JPBA.6.2. Toxicity Dose Adjustments and Delays of LY2835219

| Toxicity Type | Toxicity Profile and Severity | Dose Suspension | Dose Reduction |
|----------------------|--------------------------------|--|--|
| Hematologic Toxicity | Grade 3 | Dose MUST be suspended until toxicity resolves to at least Grade 2. | Dose reduction is NOT required. |
| Hematologic Toxicity | Recurrent ^a Grade 3 | Dose MUST be suspended until toxicity resolves to at least Grade 2. | Dose MUST be reduced by 1 dose level. |
| Hematologic Toxicity | Grade 4 | Dose MUST be suspended until toxicity resolves to at least Grade 2. | Dose MUST be reduced by 1 dose level. |

| Toxicity Type | Toxicity Profile and Severity | Dose Suspension | Dose Reduction |
|--|--|--|--|
| Hematologic Toxicity: If patient requires administration of blood cell growth factors | Regardless of severity (Use of growth factors according to ASCO Guidelines) | Dose MUST be suspended for at least 48 hours after the last dose of blood cell growth factors was administered and until toxicity resolves to at least Grade 2. | Dose MUST be reduced by 1 dose level unless already performed for incidence of toxicity that led to the use of growth factor. |
| Non-hematologic Toxicity ^b (except diarrhea, ALT/AST increased, and ILD/Pneumonitis) | Persistent or recurrent Grade 2 that does not resolve with maximal supportive measures within 7 days to baseline or Grade 1 | Dose MUST be suspended until toxicity resolves to either baseline or Grade 1. | Dose MUST be reduced by 1 dose level. |
| Non-hematologic Toxicity ^b (except diarrhea, ALT/AST increased, and ILD/Pneumonitis) | Grade 3 or 4 | Dose MUST be suspended until toxicity resolves to either baseline or Grade 1. | Dose MUST be reduced by 1 dose level. |
| Diarrhea | Grade 2 that does not resolve within 24 hours to at least Grade 1 | Dose MUST be suspended until toxicity resolves to at least Grade 1. | Dose reduction is NOT required. |
| Diarrhea | Persistent or recurrent Grade 2 that does not resolve with maximal supportive measures | Dose MUST be suspended until toxicity resolves to at least Grade 1. | Dose MUST be reduced by 1 dose level. |
| Diarrhea | Requires hospitalization or Grade 3 or 4 | Dose MUST be suspended until toxicity resolves to at least Grade 1. | Dose MUST be reduced by 1 dose level. |
| ALT/AST Increased | Persistent or recurrent ^a Grade 2 ($>3.0-5.0 \times \text{ULN}$), or Grade 3 ($>5.0-20.0 \times \text{ULN}$) ^c | Dose MUST be suspended until toxicity resolves to baseline or Grade 1. | Dose MUST be reduced by 1 dose level. |
| ALT/AST Increased | Grade 4 ($>20.0 \times \text{ULN}$) | LY2835219 therapy MUST be discontinued. | LY2835219 therapy MUST be discontinued. |
| ALT/AST Increased with increased total bilirubin, in the absence of cholestasis | \geq Grade 2 increased ALT/AST ($>3.0 \times \text{ULN}$) with total bilirubin $>2 \times \text{ULN}$ | LY2835219 therapy MUST be discontinued. | LY2835219 therapy MUST be discontinued. |
| ILD/Pneumonitis ^d | Grade 2 that persists or recurs despite maximal supportive measures and does not return to baseline or Grade 1 within 7 days | Dose MUST be suspended until toxicity resolves to baseline or Grade ≤ 1 . | Dose MUST be reduced by 1 dose level. |
| ILD/Pneumonitis ^d | Grade 3 or 4 | LY2835219 therapy MUST be discontinued. | LY2835219 therapy MUST be discontinued. |

Abbreviations: ALT = alanine aminotransferase; ASCO = American Society of Clinical Oncology; AST = aspartate aminotransferase; ILD = interstitial lung disease; ULN = upper limit of normal.

Note: MUST = mandatory.

- a Determination of persistent events will be at the discretion of the investigator. Recurrent toxicity refers to the same event occurring within the next 8 weeks (as measured from the stop date of the preceding event). As a general guidance, based on the benefit/risk balance assessment per the investigator, for a patient who experiences a new episode of Grade 3 hematologic toxicity after more than 8 weeks following the last episode of same Grade 3 hematologic toxicity, the investigator may consider resuming the patient on the same drug dose should the patient satisfy the following conditions:
 - shows stable hematologic counts (Grade ≤ 2) during that timeframe
 - has absence of any signs or risk of infection
 - is benefiting from study treatment
- b Additional guidance for renal and hepatic monitoring is provided in Sections [7.1.3.2](#) and [7.1.3.1](#).
- c Grade 3 ALT/AST increased is a trigger for additional assessments and possibly hepatic monitoring. See Section [7.1.3.1](#) for additional guidance for hepatic monitoring.
- d Additional guidance for ILD/pneumonitis monitoring is provided in Section [7.1.3.4](#).

Dose adjustments as outlined in [Table JPBA.6.3](#) are allowed both within a cycle and between cycles. LY2835219 dose alterations (omission, reduction, and discontinuation) should not be based solely on the presentation of serum creatinine values, because these may not reflect actual renal function. Further information can be found in the Section 3.2.4 of the LY2835219 IB.

If a patient who, in the judgment of the investigator, is receiving clinical benefit from study therapy requires further dose reduction than is outlined in [Table JPBA.6.3](#), then the investigator must discuss with the Lilly CRP prior to any further dose reduction.

For patients requiring dose reduction(s), re-escalation to a prior dose level is permitted only after consultation with the Lilly CRP.

Dose omissions are allowed within a cycle. If a patient requires omission of more than 25% of doses during a cycle for tolerability, then treatment may continue if the investigator determines the patient is receiving clinical benefit.

Table JPBA.6.3. Dose Adjustments of LY2835219 for Study I3Y-MC-JPBA

| Dose Adjustment | Oral Dose | Frequency |
|-----------------|-----------|----------------|
| 0 | 200 mg | Every 12 hours |
| 1 | 150 mg | Every 12 hours |
| 2 | 100 mg | Every 12 hours |
| 3 | 75 mg | Every 12 hours |

For patients in Part G with moderate hepatic impairment (defined as Child-Pugh Class B), fulvestrant 250 mg should be administered intramuscularly into the buttock slowly (1 to 2 minutes) as one 250-mg injection, according to the study schedule. In the event that fulvestrant must be discontinued, a patient may continue to receive LY2835219.

6.2.4.2. Dose Delays

Before the start of each cycle, hematologic toxicity possibly related to LY2835219 must resolve to either baseline or at least Grade 2.

Before the start of each cycle, non-hematologic toxicity (except alopecia and fatigue) possibly related to LY2835219 must resolve to either baseline or at least Grade 1.

The start of a cycle may be delayed to allow sufficient time for recovery from toxicity possibly related to study drug. Patients not recovering from such toxicity within 14 days beyond the last day of the prior cycle should be considered for discontinuation from the study.

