In addition, PK/PD modeling suggested that AUC levels associated with tumor growth delay in preclinical *in vivo* efficacy studies (approximately 3600 to 9500 ng·hr/mL) should be reached in patients within a dose range of 300 to 700 mg administered once daily ([Table JPBA.4.3](#)). Based on the *steady-state exposures* observed at the Not Severely Toxic Dose in rats and the highest Minimally Toxic Dose in dogs, the median exposure multiples predicted at steady state for this clinical dose range were approximately 8 to 18 and 0.3 to 0.7, respectively.

During the dose escalation phase, preliminary analysis of PK data from the initial 4 dose levels (50, 100, 150, and 225 mg every 24 hours) indicated less than dose-proportional increases in exposure. Based on these results, a twice daily schedule was introduced in Part A with LY2835219 administered orally at the following planned dose levels: 75, 100, 150, 200, 275, 350, and 450 mg every 12 hours for 28 days. Importantly, the first planned dose level (75 mg every 12 hours) corresponded to a daily dose of 150 mg, which was 1 dose level lower than that of the highest previously explored dose level (225 mg every 24 hours). For the twice daily schedule, the highest dose of LY2835219 evaluated was 275 mg every 12 hours. At this dose level, 2 of the 3 patients experienced DLT of Grade 3 fatigue. At the next lower dose level of 200 mg every 12 hours, 1 of the 7 patients also experienced DLT of Grade 3 fatigue. Therefore, the maximum tolerated dose (MTD) was established at 200 mg every 12 hours.

During the tumor-specific expansion phases, patients initially received LY2835219 at the MTD of 200 mg every 12 hours. A preliminary interim safety review with data from 56 patients indicated that 29 patients experienced diarrhea possibly related to study drug: 17 Grade 1 (30%), 9 Grade 2 (16%), 3 Grade 3 (5%), none Grade 4 (0%), and none Grade 5 (0%). Based on the frequency of Grade 1/2 diarrhea and the observation of clinical activity at doses below the MTD, the initial starting dose was changed to 150 mg every 12 hours with JPBA amendment (f) to gain additional PK data and clinical experience around safety/tolerability. Importantly, diarrhea experienced by patients is manageable with standard anti-diarrheal agents. Therefore, early treatment with anti-diarrheal agents (e.g., loperamide) is recommended and the initial starting dose will return to the MTD of 200 mg every 12 hours with JPBA amendment (g).

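### Section 6.2.4.2 exempts fatigue of any grade from recovery before a new cycle, while Table JPBA.6.2 mandates suspension for Grade 3/4 and for persistent or recurrent Grade 2 fatigue, and neither is given precedence

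*Protocol*

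**What the plan says.** **Start of a cycle.** Protocol Section 6.2.4.2 lists what must have recovered before each cycle. For non-hematologic events: "non-hematologic toxicity (except alopecia and fatigue) possibly related to LY2835219 must resolve to either baseline or at least Grade 1". For blood counts: "hematologic toxicity possibly related to LY2835219 must resolve to either baseline or at least Grade 2".

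**Table JPBA.6.2 (Protocol Section 6.2.4.1).** The general non-hematologic rows carve out three event types: "except diarrhea, ALT/AST increased, and ILD/Pneumonitis". Fatigue is not among them. One row is triggered by "Persistent or recurrent Grade 2 that does not resolve with maximal supportive measures within 7 days to baseline or Grade 1". The other reads "Grade 3 or 4 | Dose MUST be suspended until toxicity resolves to either baseline or Grade 1". Both rows also require reduction by one dose level. A note under the table says "Note: MUST = mandatory", although the sentence introducing the table says that it "is a guidance for management of treatment-emergent, related, and clinically significant toxicities of LY2835219".

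**Fatigue in dose escalation.** Of the highest twice-daily level tested, 275 mg, Protocol Section 4.7 reports: "At this dose level, 2 of the 3 patients experienced DLT of Grade 3 fatigue". At 200 mg every 12 hours, 1 of 7 patients had the same DLT.

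**Analysis.** SAP Section 6.3.4 summarizes doses given as planned, increased, reduced or omitted, and cycle delays, by cohort and cycle. It also summarizes drug intensity. Protocol Section 9.1.4 lists dose adjustments among the safety summaries.

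**The concern.** A patient who reaches the end of a cycle with related, clinically significant Grade 3 fatigue meets two texts. The table says that dosing must stop until recovery and resume one level lower. Section 6.2.4.2 says that fatigue need not have recovered for the next cycle to begin. A site working from the cycle-start checklist and a site working from the table could treat the same patient differently.

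Safety and tolerability are the primary objective, and Protocol Section 5.2 calls the MTD tentative pending dose confirmation. Delays, reductions and drug intensity are among the planned measures of tolerability in the expansions. If their counts for fatigue depend on which section a site followed, they are harder to interpret for the very toxicity that limited escalation.

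**Working it through.** **1. The plan's own figure.** The MTD is the highest level with less than 33% of patients having a DLT in Cycle 1 (Protocol Section 6.2.2.1). From Section 4.7:

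- 275 mg every 12 hours: 2/3 = 66.7%, not below 33%.
- 200 mg every 12 hours: 1/7 = 14.3%, below 33%.

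The stated MTD of 200 mg every 12 hours reproduces. The DLTs cited number 2 + 1 = 3, all Grade 3 fatigue.

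**2. The two rules side by side, for related and clinically significant fatigue present at the start of a cycle.**

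| Fatigue | Section 6.2.4.2 | Table JPBA.6.2 | Conflict |
|---|---|---|---|
| Grade 1 | no recovery required | no suspension row | no |
| Grade 2, not persistent or recurrent | no recovery required | no suspension row | no |
| Grade 2, persistent or recurrent, unresolved within 7 days | no recovery required | suspend to baseline or Grade 1, reduce one level | yes |
| Grade 3 or 4 | no recovery required | suspend to baseline or Grade 1, reduce one level | yes |

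**3. Do both rules govern the same decision?** Yes. In Protocol Section 6.2.1 drug is taken from Day 1 through Day 28 of each later cycle, and SAP Table JPBA 6.1 treats Day 1 of Cycle 2 and beyond as that cycle's first dose. Starting a cycle therefore means dosing. The table's title covers delays as well as adjustments, so it is not confined to events within a cycle.

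**4. Is precedence stated?** No. The table is described both as guidance and as mandatory, and neither section refers to the other on fatigue.

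**5. What one patient contributes to the summaries.** Take a patient on 200 mg every 12 hours with unresolved Grade 3 fatigue at a cycle start, no other missed doses, and recovery in time for a delayed start. SAP Section 6.3.4 defines drug intensity as actual divided by planned cumulative dose, times 100. Assume that the planned dose stays at the 200 mg level.

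- Planned for one cycle: 2 × 28 × 200 = 11,200 mg.
- Section 6.2.4.2 alone applied: 11,200/11,200 = 100%, with no delay and no reduction.
- Table applied, next level 150 mg (Table JPBA.6.3): 2 × 28 × 150 = 8,400 mg, and 8,400/11,200 = 75%, with one delay and one reduction.

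If the planned dose is instead reset to 150 mg after the reduction, intensity is 100% on both paths and only the delay and reduction counts differ. The SAP does not say which planned dose applies.

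**6. The 14-day limit.** Section 5.3.1 ties discontinuation to failure to meet the recovery criteria within 14 days and points to 6.2.4.2, where fatigue has no such criterion. Yet the sentence in 6.2.4.2 that sets the limit speaks of drug-related toxicity generally and does not repeat the fatigue exception. Whether the limit covers fatigue cannot be settled from the text.

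**7. Hematologic wording.** Section 6.2.4.2 accepts return to baseline or to Grade 2; the table's hematologic rows name only Grade 2. The two differ only for a patient worse than Grade 2 at baseline. Inclusion criterion 5 rules that out for neutrophils, platelets and hemoglobin through its entry limits, but sets none for lymphocytes, which are measured (Attachment 2).

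**The case against.** The strongest reply is that the two texts can both be obeyed. Section 6.2.4.2 waives a precondition; it does not order dosing or lift a suspension. A site that holds every patient the table tells it to hold breaks neither text, and the exemption still has work to do for Grade 2 fatigue that is neither persistent nor recurrent. Section 4.2 says the table was added to clarify modification and delay criteria, which fits that reading. This stands as far as it goes: a reader might infer two directly opposite instructions, and the documents do not support that. But the harmonizing reading is nowhere written, the exemption has no grade limit, and the table is introduced as guidance.

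Other stronger inferences also fail:

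- **That the MTD is in doubt.** It rests on Part A Cycle 1 DLTs already observed. DLTs and DLT-equivalent toxicities are defined mainly by type, grade and duration, not by cycle-start holds, so the 33% review rule in Section 6.2.3 is not defined by the disputed text.
- **That all Grade 2 or higher fatigue is affected.** Step 2 of the working shows otherwise.
- **That the 14-day limit skips fatigue.** It is unclear, no more.
- **That sites will diverge.** Nothing in the documents shows that they did. The analyses are descriptive and by cohort, without comparison of sites, and judging persistence is already left to the investigator.
- **That the hematologic mismatch is broad.** The table addresses treatment-emergent events, so a stable low baseline count does not trigger it. What remains is a patient worse than Grade 2 at baseline who worsens and then returns to baseline.

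**Conclusion.** The inconsistency is real, narrow and worth correcting. It covers related, clinically significant fatigue of Grade 3 or 4, and persistent or recurrent Grade 2 fatigue unresolved within 7 days, present at the start of a cycle. For these patients the protocol supports either holding or redosing, depending on the section read, and states no precedence.

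Its possible effect is on the dose-delay, dose-reduction and drug-intensity summaries. Its importance comes from fatigue having been the event in all three cited DLTs. How many cycles are touched cannot be computed, because the documents give no frequency of such fatigue in the expansions. Nor do they say how many cycles were started after the table entered the protocol with amendment (h).

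The conclusion assumes that the fatigue exemption means what it says, without an implied grade limit, and that the general non-hematologic rows cover every event they do not except. No view is taken on which clinical rule is right.

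**What to change.** - **Protocol.** Reconcile Section 6.2.4.2 with Table JPBA.6.2 so that one stated rule governs related fatigue at the start of a cycle. Which rule is for the sponsor and investigators to decide. State in Sections 5.3.1 and 6.2.4.2 whether the 14-day recovery limit applies to fatigue.
- **SAP Section 6.3.4.** In the dose-administration summary, flag cycles started with unresolved related fatigue that was Grade 3 or 4, or persistent or recurrent Grade 2 in the table's sense, so that data gathered under the present text can be interpreted. A flag on all Grade 2 or higher fatigue would catch cycles that comply with both texts.
- **Minor.** Use the same hematologic recovery condition, with or without return to baseline, in both places.

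The cost is a short protocol clarification and one derived flag from adverse-event and dosing data already collected. No new assessments are needed and the sample size does not change.

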6.3. Method of Assignment to Treatment

Patients who meet all criteria for enrollment will be assigned to receive LY2835219 in this study. Prior to enrollment into the study, an eligibility check must be conducted (for every patient) between the investigational site and the Lilly clinical research personnel, to confirm that the patient meets all enrollment criteria. Upon confirmation of eligibility, the sponsor will confirm the dose, cohort, and identification number assignment for each patient. No patients can be enrolled into the next cohort without prior discussion and agreement with the responsible Lilly CRP.

6.3.1. Continued Access

Participants who are still on study drug may continue to receive study drug during the continued access period if they are experiencing clinical benefit and no undue risks. Lilly will notify investigators when the continued access period begins. Lilly may allow participants to enroll in a “rollover” protocol to provide long-term continued access for participants enrolled in this study.

Patients are not required to sign a new informed consent form (ICF) before treatment is provided during the continued access period.

During the continued access period, all adverse events (AEs), serious adverse events (SAEs), and study drug exposure will be reported on the case report form (CRF). Serious adverse events will also be reported to Lilly Global Patient Safety (see Section 7.1.2). In the event that an SAE occurs, Lilly may request additional information (such as local laboratory results, concomitant medications, and hospitalizations) in order to evaluate the reported SAE.

Investigators will perform any other standard procedures and tests (locally) needed to treat and evaluate patients; however, the choice and timing of the tests will be at the investigator’s discretion. Lilly will not routinely collect the results of these assessments.

The patient’s continued access to study drug will end when a criterion for discontinuation is met (Section 5.3). Continued access follow-up will begin the day after the patient and investigator agree to discontinue study drug and last approximately 30 days.

Patients who are in short-term follow-up when the continued access period begins will continue in short-term follow-up until the 30-day short-term follow-up visit is completed.

In all cases, no follow-up procedures will be performed for a patient who withdraws informed consent unless he or she has explicitly provided permission and consent.

6.4. Blinding

This is an open-label study.

